location by the co-investigator and unknown to the PI. The patients assigned to the Brace group will receive a standard postoperative hip brace at their preoperative visit with the Physician Assistant, billed to the Research Account (~\$290/brace). Patients in the Brace group will be expected to wear their braces at all times for the initial 3-week period except shower and toilet, as per current standard of care. Patients in both groups will be prescribed our standardized physical therapy protocol for arthroscopic hip osteoplasty and labral repair. All data will be stored in a de-identified, secure server maintained by the research coordinator and PI (REDcap). As all patients will have discontinued their braces by the 6-week visit this will be a single-blinded trial; the PI - who will be analyzing patient reported outcome measures and performing each exam at the 6-week visit - will have no knowledge of patient assignment. Any patient care questions will be managed by the Physician Assistant and nursing team so as to ensure no accidental exposure of the PI to a question about bracing.

Statistical Analysis, Feasibility, Safety: As short-term NPRS scores are absent in the literature for hip arthroscopy, sample size has been calculated using 2-years of pilot data on 6-week postoperative NPRS scores for FAIS patients (all wore braces) in the PI's practice, demonstrating a mean NPRS of 2.4 (SD 1.7). Given the cost of hip bracing, a treatment effect size of 50% increase in pain in the No Brace group (mean NPRS 1.2 higher) is used with 1:1 enrollment ratio and standard two-sided alpha of 0.05 and beta of 0.20,

resulting in a total of 32 patients per group. Assuming a 10% drop out this would be 36 patients per group. Baseline and postoperative data will be compared using Fisher exact test and *t* testing.

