The PI is the only provider in the UWMC system who performs hip arthroscopy and in order to contain cost this will be a single-center study. The PI currently performs approximately 50-75 hip arthroscopies for FAIS per year. A pilot feasibility questionnaire was administered to 18 hip patients over a 3-month period with 17/18 (94%) responding favorably to participate in the trial. We expect high follow-up rates at 6 weeks as in the PI's current practice this rate is 94.7% among FAIS patients. We thus anticipate enrollment and 6-week results to be complete within 2 years, with pilot data within 1 year. During the study period we will monitor for any serious adverse effects including hip dislocation, revision surgery, or intractable pain. These will be promptly reported to the IRB and trial sponsor.

Strengths & Weaknesses: This study is innovative as there are no evidence-based reports on bracing after hip arthroscopy. This study is important because of the cost of bracing and frequency of hip arthroscopy. There is excellent equipoise as approximately 50% of surgeons use postoperative hip braces. This study also would add to its field by providing short term postoperative pain data as well as high quality data on incidence of IPT after hip arthroscopy. If the null hypothesis is shown and there are no differences between groups, we could justify disuse of hip braces and reduce societal costs. The most obvious weakness lies in the ability to recruit and meet sample size requirements. In case of poor enrollment, we will use

these data as an internal pilot study, to refine group variability/event rates and expand to a multicenter trial (the PI has already received interest from several academic centers that wish to participate), with hope for extramural funding.

References

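### Does the poor-enrollment fallback to an internal pilot push the type I error above 0.05?

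*Combined protocol and SAP*

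**What the plan says.** The fallback is one sentence under Strengths & Weaknesses. If enrollment is poor, the sponsor would use "these data as an internal pilot study, to refine group variability/event rates and expand to a multicenter trial". The same sentence mentions interest from other academic centers and the hope of outside funding. Under Statistical Analysis, Feasibility, Safety the timeline reads: "We thus anticipate enrollment and 6-week results to be complete within 2 years, with pilot data within 1 year".

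The error rate at stake is the one behind the NPRS sample size in that section: "standard two-sided alpha of 0.05 and beta of 0.20", equal allocation, a difference of 1.2 points and an SD of 1.7, "resulting in a total of 32 patients per group", or 36 after 10% dropout. The stated tests are Fisher exact and t tests.

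The Approach section leaves the randomization key with a co-investigator. The PI, who analyzes the patient-reported outcomes and does the 6-week examinations, is not to know the assignments.

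The plan does not say whether the re-estimation is pooled or by arm, what rule resets the sample size, what the maximum is, or whether the first patients enter the final test. Nor does it say whether the multicenter study is this trial enlarged or a new one.

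**The concern.** Three features together look like an uncontrolled adaptive design. An internal pilot by its usual meaning keeps its data. The word group can be taken to mean arm, and for the binary secondary outcomes (antalgic gait, iliopsoas signs, narcotic refills) a rate in each arm is the treatment effect, not a nuisance quantity. Data are also expected at one year, halfway through, with no stated limit on who sees them or in what form.

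If arm results were opened and the decision to expand, or the new size, depended on them, a final unadjusted test at 0.05 on all the data would reject a true null too often. If the PI saw those results, later gait and palpation findings could also be colored by them. The fallback is a real prospect, since the plan itself names recruitment as its most obvious weakness.

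**Working it through.** **Reproducing the plan's figure.** The inputs, all from Statistical Analysis, Feasibility, Safety, are difference 1.2, SD 1.7, two-sided alpha 0.05, power 0.80 and ratio 1:1.

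n per group = 2 × (1.960 + 0.842)² × 1.7² / 1.2² = 15.70 × 2.89 / 1.44 = 31.5, so 32. With dropout, 32 / 0.90 = 35.6, so 36. Both match the plan. (The t-based calculation gives 32.5, hence 33, with power 0.794 at 32. The gap is immaterial.)

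**Type I error under different readings.** The plan gives no look size, rule or cap, so these are assumptions: pilot of 10, 16, 20 or 24 per arm; normal outcome, SD 1.7, no true difference; 1,000,000 replicates per pilot size (Monte Carlo standard error 0.0002); and an unadjusted pooled t test at 0.05 on all the data.

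With the difference kept at 1.2, the new size is N = 15.70 × s² / 1.2² = 10.9 × s² per arm. Here s² is either the blinded variance of the mixed sample or the within-arm variance. If the observed difference d drives the size, N = 15.70 × s² / d², held between 32 and a cap of 64, 100 or 150 per arm.

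| Rule | Type I error |
|---|---|
| Blinded SD, difference kept at 1.2 | 0.049–0.050 |
| Within-arm SD, difference kept at 1.2, N at least 32 | 0.051 |
| Within-arm SD, difference kept at 1.2, N may also fall | 0.053–0.056 |
| Arm results seen, expansion to a fixed 64 per arm regardless | 0.050 |
| N set from the observed difference, 32 up to the cap | 0.058–0.072 |
| Test at the pilot and again at a final 32, 64 or 150 per arm | 0.074–0.096 |

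For the one-year data, unadjusted tests at 18 and then 36 per arm (correlation √(18/36) = 0.71) would give 8.3%.

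**Matching rules to text.** The first three rows resize on variability, which the fallback sentence names and which is a nuisance parameter for NPRS. The fourth row shows that seeing arm results and keeping the data is not enough to raise the error: if the final size does not depend on the results, the last test is an ordinary fixed-sample test. The last two rows and the 8.3% need a rule that the documents do not contain.

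**The case for a change.** The strongest case on the other side is that the plan does not choose among these readings. Control of the error at 0.05 therefore rests on good sense rather than on a written rule, and a sentence or two would settle it. The planning SD also comes only from braced patients, so a re-estimate may well matter.

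Much of that stands. The contingency is under-specified, and rates by arm would reveal the effect on the binary secondary outcomes. The simulation covers NPRS only and says nothing about Fisher tests on those outcomes.

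The stronger claims do not stand. No text opens results by arm or attaches a comparison or decision to the one-year data, which appear in a feasibility timeline. The stated trigger is enrollment, so expansion because early results look promising runs against the wording. Exposure of the PI would contradict the Approach section, and nothing lifts that blinding for the fallback. The event-rate argument concerns secondary outcomes, while the 0.05 is stated for the NPRS calculation. The source of the planning SD is a question of power, not of type I error.

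**Conclusion.** The concern does not call for a change. It describes a gap in a one-sentence contingency that an analyst would ordinarily fill in the harmless way: keep the difference at 1.2, re-estimate the SD, and make no efficacy comparison at that point. On that reading the type I error for NPRS is 0.049 to 0.051, or at most about 0.056 if the within-arm SD is used and the sample size is allowed to fall. Error of 0.058 to 0.072, or 0.074 to 0.096, would need resizing on the observed difference or an unadjusted test of the pilot, and the plan states neither.

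These figures rest on normal outcomes, an assumed look at 10 to 24 per arm and a final size of at most 150 per arm. The conclusion would differ if the sponsor did size the expansion from arm-level results and pooled the data.
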